5.6.1 TAK-659 Administration

TAK-659, should be taken on an empty stomach at least 1 hour before and no sooner than 2 hours after ingestion of food and/or beverages other than water. Each tablet should be swallowed separately with a sip of water. A total of approximately 8 ounces (240 mL) of water should be taken with the prescribed doses of TAK-659. Patients must swallow the tablets whole; the tablets must not be chewed, crushed, or manipulated in any way before swallowing.

Patients should be instructed to take their study medication at approximately the same time each day and to not take more than the prescribed dose at any time. If a patient fails to take TAK-659 one day, or if a patient does not take TAK-659 at their scheduled dosing time (\pm 6 hours of the scheduled dosing time), that dose should be skipped, and the patient must not make dose adjustments to account for the missed dose on subsequent days, for example, by taking a double dose of study drug(s) on the following day. Patients should record any skipped doses in their dosing diary (and resume dosing at the next scheduled time with the prescribed dosage).

If severe emesis prevents the patient from taking a TAK-659 dose, that dose will be skipped. If emesis occurs after TAK-659 ingestion, patients should not re-dose following emesis and should record the time of the emesis in their dosing diary. Patients should resume dosing at the next scheduled time with the prescribed dosage.

On clinic visit days, patients should be instructed to hold their dose until pre-dose assessments are performed. The timing of the visit should be planned so that the pre-dose PK draw occurs near the same time as the previous day's dosing. TAK-659 administration guidelines described above will still be followed on clinic days. On clinic days for PK determination, TAK-659 will be taken first and then Ixazomib. Patients should be instructed to return their empty blister packs to the clinic, rather than discarding them. Reconciliation will occur accordingly when the patient returns for their next cycle of take-home medication.

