5.6.2 Ixazomib Administration

Ixazomib should be taken once a week on the same day and at approximately the same time for the escalating cycle. Ixazomib should be taken at least one hour before or at least two hours after food. The whole capsule should be swallowed with water. A total of approximately 8 ounces (240 mL) of water should be taken with the capsules. Patients should be instructed to store the medication between $+2^{\circ}\text{C}$ and $+30^{\circ}\text{C}$ (35.6°F - 86°F) for the duration of each cycle. Do not freeze Ixazomib or store above 30°C . Any extreme in temperature should be reported as an excursion and should be dealt with on a case-by-case basis.

The capsule should not be crushed, chewed or opened.

If an Ixazomib dose is delayed or missed, the dose should be taken only if the next scheduled dose is \geq 72 hours away. A missed dose should not be taken within 72 hours of the next scheduled dose. A double dose should not be taken to make up for the missed dose. If the patient vomits after taking a dose, the patient should not repeat the dose but should resume dosing at the time of the next scheduled dose. On clinic visit days, patients should be instructed to hold their dose until pre-dose assessments are performed. Ixazomib administration guidelines described above will still be followed on clinic days. On clinic days for PK determination, TAK-659 will be taken first and then Ixazomib.

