7. STUDY CALENDAR: DOSE ESCALATION COHORTS (PHASE 1)

	Screen	Cycle 1				Cycles 2-4			Cycles 5+			Safety follow up	Long-term follow up	
		-28 days ¹	D 1	D 4	D 8	D 15	D 1	D 8	D 15	D 1	D 8	D 15		
Cycle = 21 days														
REQUIRED ASSESSMENTS														
Informed consent ⁴ , Eligibility criteria	X													
Medical history, Disease characteristics	X	X												
Physical exam ⁵	X	X ⁵		Sx	Sx	X		Sx	X				X	
Ophthalmic Exam ⁶	X					C2				C7D1; q6			X	
Height (screen only); Weight	X	X				X				X			X	
Vital signs (BP, pulse, temperature)	X	X		X	X	X		X	X				X	
ECOG Performance status	X	X				X				X			X	
12-lead ECG ⁷	X	×2			×2				X	X			X	
AEs & concomitant medications ⁸		X		X	X	X		X	X				X	
Drug Diary Review		X		X	X	X				X			X	
LABORATORY ASSESSMENTS⁹														
CBC with diff, platelets, ANC. Chemistry ¹⁰	X	X ¹⁰	X	X ¹⁰	X	X	C2	X	X				X	
Uric acid, Mag, Amylase, Lipase, GGT ¹⁰	X	X ¹⁰	X	X ¹⁰	X	X		X	X				X	
Urinalysis	X				X	X		X	X				X	
Pregnancy test for WOCBP ¹¹	X	X				X				X				
DISEASE ASSESSMENT														
NGS results or submit for NGS testing	X													
Bone marrow biopsy and aspirate ¹²	X				X			C2,4	as indicated					
TREATMENT EXPOSURE														
TAK-659 (Daily ×15 days)			D1-15				D1-15			D1-15				
Ixazomib (Days 1, 8, 15)	X		X	X		X	X	X	X	X	X			
CORRELATIVE STUDIES (SPECIMEN COLLECTION)														
Buccal swab for germline DNA analysis		X												
Bone marrow aspirate for biomarker analyses and PD	X			X ¹³	X			C2,4						
Serum for proteomic analysis		X	X											
Plasma for PK ¹⁴		×2			×2			×2						
BANKING SAMPLES (SPECIMEN COLLECTION)														
Whole Blood ¹⁵		X												
Serum and Plasma ¹⁵		X										X		
FOLLOW-UP														
Survival status, subsequent therapy													X	

Phase I calendar footnotes:

Evaluations/laboratory assessments performed on visit days will occur before dosing unless otherwise indicated. On these days, patients will be instructed to hold dosing until relevant assessments have been completed.

1. Screening assessments performed within 3 days before Cycle 1 Day 1 do not need to be repeated, unless otherwise specified.
2. Safety follow up visit will occur 30 days (+10 days) after the last dose of study drug or before the start of subsequent anticancer therapy (other than hydroxyurea) whichever occurs first.

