11. Women of childbearing potential: A serum pregnancy test will be done at screening. A urine pregnancy test will be done predose D1 of all cycles, with negative results available prior to dosing. If a negative serum test is done within 3 days of C1D1, the C1D1 urine test will be waived.
12. Bone marrow biopsy and aspirate for disease burden (blast counts), cytogenetics, and cellular composition by flow cytometry will be done at screening. In addition, BM biopsies and/or aspirates will be done to assess disease response at Cycles 1, 2, and 4 between Days 15-21, provided the results are available before Day 1 of the next cycle. After Cycle 4, BM biopsy and/or aspirate assessment will be performed as clinically indicated based on changes in peripheral blood counts, or when it is needed to establish either CR or disease progression. NOTE: a BM biopsy is required only at screening. Residual and/or additional bone marrow samples will be requested for biomarker analysis. In cases when insufficient bone marrow aspirate is collected, peripheral blood will be collected and submitted per the instructions in the CLM.
13. Bone marrow will be done at C1D4 for the 1st 5 patients. Thereafter, BM timing (D4 vs 8) will be determined from the results in the first 5 patients.
14. Blood for PK plasma samples will be collected at: C1D1 (pre-dose, 2-4 hr post-dose), C1D15 (pre-dose, 2-4 hr post-dose), Cycle 2, 3, 4 Day 15 (pre-dose, post-dose anytime during clinic visit). Instruct patient to withhold study drug(s) for that day. The timing of the visit should be planned so that the pre-dose PK draw occurs near the same time as the previous day's dosing. When a blood sample coincides with the timing of an ECG, the ECG will be completed first. Refer to the CLM for detailed instructions on collection, processing, storing, and shipping of PK samples.
15. Whole blood for banking is to be collected at pre-dose C1D1. Serum and plasma for banking are to be collected at pre-dose C1D1 and at the 30-Day Safety Follow up visit. See CLM for collection, processing, labeling and shipping instructions.

8. STUDY CALENDAR: PHASE 2

Cycle = 21 days	Screen	Cycle 1				Cycles 2-4			C 3	Cycles 5+			Safety follow up	Long-term follow up
	-28 days ¹	D 1	D 4	D 8	D 15	D 1	D 8	D 15	D 22	D 1	D 8	D 15	30 days post Tx ²	Q month (±14) ³
REQUIRED ASSESSMENTS														
Informed consent ⁴ , Eligibility criteria	X													
Medical history, Disease characteristics	X	X												

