Physical exam ⁵	X	X ⁵		Sx	Sx	X		Sx		X				X
Ophthalmic Exam ⁶	X					C2				C7D1; q6				X
Height (screen only); Weight	X	X				X				X				X
Vital signs (BP, pulse, temperature)	X	X		X	X	X		X		X				X
ECOG Performance status	X	X				X				X				X
12-lead ECG ⁷	X	X						X		X				X
AEs & concomitant medications ⁸		X			X	X		X		X				X
Drug Diary Review		X			X	X				X				X
LABORATORY ASSESSMENTS⁹														
CBC with diff, platelets, ANC. Chemistry ¹⁰	X	X ¹⁰	X	X ¹⁰	X	X	C2	X		X				X
Uric acid, Mag, Amylase, Lipase, GGT ¹⁰	X	X ¹⁰	X	X ¹⁰	X	X		X		X				X
Urinalysis	X			X		X		X		X				X
Pregnancy test for WOCBP ¹¹	X	X				X				X				
DISEASE ASSESSMENT														
NGS results or submit for NGS testing	X													
Bone marrow biopsy and aspirate ¹²	X				X				C3D22 ¹²	as indicated				
TREATMENT EXPOSURE														
TAK-659 (Daily ×15 days)			D1-15			D1-15			D1-15					
Ixazomib (Days 1, 8, 15)		X		X	X	X	X	X		X	X	X		
CORRELATIVE STUDIES (SPECIMEN COLLECTION)														
Buccal swab for germline DNA analysis		X												
Bone marrow aspirate for biomarker analyses and PD	X		X ¹³		X				C3D22 ¹²	@ PD ¹³				
Serum for proteomic analysis		X	X											
Plasma for PK ¹⁴		×2			×2			×2						
BANKING SAMPLES (SPECIMEN COLLECTION)														
Whole Blood ¹⁵		X												
Serum and Plasma ¹⁵		X											X	
FOLLOW-UP														
Survival status, subsequent therapy														X

Phase II calendar footnotes: Evaluations/laboratory assessments performed on visit days need to take place before dosing unless otherwise indicated. On these days, patients should be instructed to hold dosing until relevant assessments have been completed.

1. Screening assessments performed within 3 days before Cycle 1 Day 1 do not need to be repeated, unless otherwise specified.
2. Safety follow up visit will occur 30 days (+10 days) after the last dose of study drug or before the start of subsequent anticancer therapy (other than hydroxyurea) whichever occurs first.
3. All patients, including those no longer on treatment, will be followed for survival. Patients who discontinue the study will be followed for survival every month for up to 12 months after discontinuation of the study drug until death, loss to follow-up, or withdrawal of consent. Information on subsequent anticancer therapies will also be collected. For patients who achieve CR but discontinue study treatment while still in remission, disease progression based upon available local data will also be collected.

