12. Bone marrow biopsy and aspirate for disease burden (blast counts), cytogenetics, and cellular composition by flow cytometry will be done at screening. In addition, BM aspirates and/or biopsies will be done to assess disease response at Cycle 1 Day 15 and Cycle 3 Day 22, so that the results are available before Day 1 of the next cycle. In the post-Cycle 3 assessment, aspirate and biopsy are suggested on day 22 (or within 3 days prior to C4D1), simultaneous with the plan to continue onto C4 D1, to serve as record establishing the optimal response/composite CR. Such planning should be guided by the trend of blast reduction observed during Cycles 1, 2. After Cycle 3 assessment, BM biopsy and/or aspirate assessment will be performed as clinically indicated based on changes in peripheral blood counts, or when it is needed to establish either CR or disease progression. NOTE: a BM biopsy is required at screening and post-Cycle 3 D22. Residual and/or additional bone marrow samples will be requested for biomarker analysis. In cases when insufficient BM aspirate is collected, peripheral blood will be submitted per the instructions in the CLM.
13. BM timing (D4 vs D8) will be determined from results in the Phase I patients. At the time of relapse (PD) of any patient who had initially responded to TAK-659, bone marrow aspirate and/or biopsy materials will be collected for biomarker study.
14. Blood for PK plasma samples will be collected at : C1D1 (pre-dose, 2-4 hr post-dose), C1D15 (pre-dose, 2-4 hr post-dose), Cycle 2, 3, 4 Day 15 (pre-dose, post-dose anytime during clinic visit). Instruct patient withhold study drug(s) for that day. The timing of the visit should be planned so that the pre-dose PK draw occurs near the same time as the previous day's dosing. When a blood sample coincides with the timing of an ECG,

the ECG will be completed first. Refer to the CLM for detailed instructions on collection, processing, storing, and shipping of PK samples.

15. Whole blood for banking is to be collected at predose C1D1. Serum and plasma for banking are to be collected at pre-dose C1D1 and at the 30-Day Safety Follow up visit. See CLM for collection, processing, labeling and shipping instructions.

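### Footnote 14 of both study calendars withholds study drug for the whole of each PK day, contradicting Sections 5.6.1 and 5.6.2, the calendar headers and the postdose samples and ECGs due on those days

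*Combined protocol and SAP*

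**What the plan says.** Footnote 14 of the Phase 1 calendar (Section 7) lists the plasma PK draws and then says "Instruct patient to withhold study drug(s) for that day". Footnote 14 of the Phase 2 calendar (Section 8) has the same sentence with a word missing: "Instruct patient withhold study drug(s) for that day". The listed days are Cycle 1 Day 1 and Day 15 of Cycles 1 to 4. Each has a predose and a postdose sample; for the Day 15 visits the footnote reads "C1D15 (pre-dose, 2-4 hr post-dose), Cycle 2, 3, 4 Day 15 (pre-dose, post-dose anytime during clinic visit".

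Other places say something different about the same days:

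- Section 5.6.1 (TAK-659): "On clinic visit days, patients should be instructed to hold their dose until pre-dose assessments are performed". Section 5.6.2 gives ixazomib the same rule.
- Section 5.6.2, and also 5.6.1, the 5.6 table and the cohort tables in 5.2: "On clinic days for PK determination, TAK-659 will be taken first and then Ixazomib".
- The header above the Phase 1 calendar footnotes: "On these days, patients will be instructed to hold dosing until relevant assessments have been completed". The Phase 2 header: "On these days, patients should be instructed to hold dosing until relevant assessments have been completed".
- Phase 1 footnote 7 schedules an ECG 3 hours after the dose on Cycle 1 Days 1 and 15. All other Phase 1 ECGs are predose.
- The treatment rows of both calendars schedule both drugs on Days 1 and 15.

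**The concern.** A hold until the predose draw and a hold for the whole day are different dosing instructions. The second cannot coexist with a postdose sample on that day. A site or patient who follows the footnote as written omits or postpones doses on the days that supply Phase 1 decision data.

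Four things are exposed. The PK criterion in Section 5.3 uses a TAK-659 peak on Day 1 and Day 15. The postdose ECGs on Cycle 1 Days 1 and 15 are the only ones scheduled in Phase 1. The DLT-evaluable population in Section 13.4 requires at least 75% of planned doses within two cycles, absent a Cycle 1 DLT. The tolerability criterion in Section 5.3 requires more than 80% of the expected dose. Ixazomib is the only drug being escalated (Section 5.2), and with three doses per cycle its dose fraction is sensitive to a single omission.

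**Working it through.** The plan gives no figure to reproduce. The check compares the passages and then counts doses.

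**Can the instructions be reconciled as written?** No. Sections 5.6.1 and 5.6.2 and both headers end the hold once assessments are done, whereas footnote 14 extends it to the whole day. Footnote 14 also conflicts with its own postdose samples and, in Phase 1, with footnote 7. Its next sentence, on timing the predose draw close to the previous day's dosing time, also appears in Section 5.6.1. There it follows the hold-until-assessments instruction, which suggests the footnote is a clipped version of that text.

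**Inputs.** TAK-659 is given on Days 1-15 (15 doses per cycle) and ixazomib on Days 1, 8 and 15 (3 doses per cycle), from Section 5. The PK days come from footnote 14 and Section 8.4.

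**Doses left on the literal reading, with no late dose taken.** Fraction = (planned doses − doses falling on PK days) / planned doses.

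| Window | Drug | Day 15 doses lost | Day 15 and C1D1 lost |
|---|---|---|---|
| Cycles 1-2 | Ixazomib | (6−2)/6 = 66.7% | (6−3)/6 = 50.0% |
| Cycles 1-2 | TAK-659 | (30−2)/30 = 93.3% | (30−3)/30 = 90.0% |
| Cycles 1-4 | Ixazomib | (12−4)/12 = 66.7% | (12−5)/12 = 58.3% |
| Cycles 1-4 | TAK-659 | (60−4)/60 = 93.3% | (60−5)/60 = 91.7% |

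Under the hold described in Sections 5.6.1 and 5.6.2, no planned dose is lost: 6/6 and 30/30 over two cycles.

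**Against the thresholds, counting each drug separately.** Ixazomib at 66.7% or 50.0% is below both 75% (Section 13.4) and >80% (Section 5.3). TAK-659 at 90.0-93.3% is above both.

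**Could the doses be recovered?** Section 5.6.2 lets a delayed or missed ixazomib dose be taken if the next is at least 72 hours away. From Day 15 to Day 1 of the next 21-day cycle is (22−15)×24 = 168 h, or (22−16)×24 = 144 h from Day 16. From Day 1 to Day 8 is (8−1)×24 = 168 h. The rule would therefore allow a late dose in every case. TAK-659 has no such rule: under Section 5.6.1 a dose outside the ±6 hour window is skipped.

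**PK and ECG.** A late ixazomib dose does not restore the TAK-659 postdose sample or the 3-hour ECG. Without a TAK-659 dose that day, no sample measures the peak named in Section 5.3.

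**The case against.** The strongest reply is that no site would read the sentence literally. The calendar header just above, the postdose samples in the same footnote, the postdose ECGs and the treatment rows all presuppose dosing on those days. On Cycle 1 Day 1 the literal reading would withhold the first dose on the day treatment starts. The natural meaning is that patients should not take the drug before coming to clinic. Footnote 14 also refers sites to the Correlative Laboratory Manual, which is not among these documents and may be clearer.

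Much of this stands. The intended design is recoverable from the surrounding text, so this is an internal contradiction and not a design choice, and the percentages are not a forecast. It does not dispose of the point: the sentence is explicit and appears in both phases.

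A reader might infer more than the documents support:

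- *That the footnote necessarily removes the Day 15 ixazomib dose.* The 72-hour rule in Section 5.6.2 allows it to be taken late. The 67% and 50% figures hold only if it is not.
- *That Day 15 postdose samples would be drug-free.* Section 1.4.2.1 reports a TAK-659 half-life of 34.4 hours and mean accumulation of 1.90- to 2.54-fold after 15 days of daily dosing. A Day 15 sample would contain drug; it would simply not be a postdose peak. Only the Cycle 1 Day 1 sample would be drug-free.
- *That the missed doses would count as DLTs.* The 75% criterion in Section 5.4 covers only omissions due to related toxicity.
- *That the Cycle 2-4 samples feed the recommended-dose decision.* The Section 5.3 criterion names Day 1 and Day 15 without giving a cycle.

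**Conclusion.** The contradiction is real, and it covers Cycle 1 Day 1 and TAK-659 as well as the Day 15 ixazomib doses. It should be corrected, although the likely intent is benign.

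If the footnote is followed literally, the certain losses are the valid postdose TAK-659 samples, the Phase 1 postdose ECGs on Cycle 1 Days 1 and 15, and one TAK-659 dose per PK day. The ixazomib shortfall is a conditional worst case. It assumes that the site follows the footnote, that no late dose is taken under Section 5.6.2, and that both thresholds apply to each drug separately.

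The last assumption matters because neither Section 13.4 nor Section 5.3 states it. Pooling the dose counts of the two drugs would give (28+4)/36 = 88.9%, or (27+3)/36 = 83.3% with Cycle 1 Day 1 included, above both thresholds.

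**What to change.** Reconcile footnote 14 in both calendars with Sections 5.6.1 and 5.6.2 and with the calendar headers, so that one instruction states when each drug is taken relative to the predose draw, the postdose draw and, in Phase 1, the postdose ECG. Check that the Correlative Laboratory Manual carries the same instruction. If any patient has already been sampled under the current text, confirm from the dosing diaries whether PK-day doses were taken, and when, before using those samples or dose fractions. The amendment costs one sentence in two footnotes and leaves the sample size, visit schedule and analyses unchanged.

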8.1 Study Procedures

Patients will be evaluated at scheduled visits over the following study periods: Screening, Treatment, and Safety Follow up. Evaluations during the Screening period are to be conducted within 28 days before administration of the first dose of study drug. Procedures conducted during the Screening period that are performed within 3 days of Cycle 1, Day 1 may also be used as the predose evaluation and do not need to be repeated, unless otherwise specified.

The timing of PK, PD, and proteomic assay assessments is specified in the Schedule of Events and is not flexible. Other laboratory assessments and procedures may occur within -3 days before the scheduled day, and Day 1 of Cycle 2 and beyond may be modified by up to 3 days due to extenuating circumstances (ie, inclement weather, holidays, vacations, or other administrative reasons).

Medical History

During the Screening period, a complete medical history will be compiled for each patient. The history will emphasize the background and progress of the patient's malignancy and include a description of prior therapies received. Sites will be required to record any screening reports on tumor cytogenetics and/or mutation assays (eg, FLT-3, and NGS) performed as part of the standard of care.

Physical Examination

A physical examination (PE) will be completed per standard of care at the times specified in the Schedule of Events. During dose escalation, complete PEs will be performed at screening, Day 1 of each cycle of treatment, and safety follow up. Symptom- or finding-directed PEs will be performed on Day 8 and 15 of Cycle 1 and Day 15 of Cycles 2, 3, and 4.

Note: Physical examinations at screening will include a neurological examination.

Height and Weight

Height will be measured only during screening (within 28 days before the first dose of TAK-659). Weight will be measured during the times specified in the Schedule of Events.

Vital Signs

Vital sign measurements include diastolic and systolic blood pressure, heart rate, and temperature, and will be assessed as specified in the Schedule of Events. Blood pressure should be determined with the patient in a seated position after the patient has been sitting quietly for approximately 5 minutes.

Pregnancy Test

A serum pregnancy test will be performed for women of childbearing potential at screening. A urine pregnancy test will be performed predose on Day 1 of all cycles with negative results available before the first dose may be administered. If the serum pregnancy test is performed within 3 days from the first dose and the result is negative, the urine pregnancy test on Cycle 1, Day 1 may be waived.

Concomitant Medications and Procedures

Concomitant medications and procedures will be recorded in the eCRF from the time of the first dose of study drug through 30 days after the last dose of study drug or to the start of subsequent anticancer

therapy, whichever occurs first. See Section 5.8 for a list of medications and therapies that are allowed/prohibited during the study.

Electrocardiogram

12-lead ECGs will be performed and interpreted locally. The ECG schedule is more intensive for patients enrolled in the dose escalation cohorts. The time points for ECG collection may be revised based on emerging PK data, but the number of time points will not increase.

All scheduled ECGs should be performed pre-dose, unless otherwise specified, and after the patient has rested quietly for at least 5 minutes in a supine position. When the timing of a PK, PD, PIA or safety laboratory blood sample coincides with the timing of ECG measurements, the ECG will be completed before the collection of the blood sample. In some cases, it may be appropriate to repeat an abnormal ECG to rule out improper lead placement as contributing to the ECG abnormality.

Estimates of QTc for study eligibility should use QT correction formula (QTcF). In the event that a QTc value confirmed by the qualified reader is >475 msec, an evaluation to determine etiology should be conducted. If the prolonged QTc finding can be corrected based on change in medication and/or corrections of electrolyte abnormalities, and a repeat ECG meets eligibility requirements, the patient may enroll to the study upon review and agreement by the sponsor investigator.

Following initiation of treatment, if a QTc value is confirmed as >500 msec for any ECG, the following will occur:

- The sponsor investigator will be promptly notified.
- TAK-659 should be held and an evaluation should be conducted to correct other possible causes (eg, electrolyte disturbance, concomitant medication).
- Additional ECGs may be performed at more frequent intervals until repeated QTc measurements fall or are below the threshold interval that triggered the repeat measurement.

The decision whether to reinitiate TAK-659 treatment with or without dose reduction and additional monitoring in those patients who had asymptomatic prolonged QTc > 500 msec (Grade 3) that has reverted to an acceptable interval, have previously tolerated TAK-659, and appear to have benefitted from TAK-659 treatment with either disease control or response will be agreed to by the local investigator and the sponsor investigator on a case-by-case basis.

The ECGs performed should be reviewed by the local investigator or his/her delegate before the patient leaves the clinic on visit days.

Hematology

Will include: Hemoglobin; Leukocytes with differential; Hematocrit; Neutrophils (absolute neutrophil count [ANC]); Platelet (count); Percentage of leukemic blast cells

Serum Chemistry

Will include: Blood urea nitrogen (BUN); Albumin; Calcium; Alkaline phosphatase; Chloride; Creatinine; Carbon dioxide (CO₂); Bilirubin (total) Aspartate aminotransferase (AST); Alanine aminotransferase (ALT); Uric acid; Magnesium; Lactate dehydrogenase (LDH); Amylase; Lipase; Total protein; Gamma glutamyl transferase (GGT); Glucose; Phosphate; Sodium; Potassium

Urinalysis

Turbidity and Color; Ketones; Urobilinogen; pH; Bilirubin; Glucose; Specific gravity; Occult Blood; Leukocytes; Protein; Nitrite

Ophthalmic Exam

A slit lamp eye examination will be performed by an ophthalmologist at Screening; on Cycle 2 Day 1; on Cycle 7 Day 1; every 6 cycles thereafter (+/- 2 weeks); and at the Safety follow up. On the basis of nonclinical toxicology findings with TAK-659 in rats, slit lamp examinations should focus on detecting any posttreatment changes in ocular lens. Examination and photographing of the retina will be performed at baseline but not during the study unless clinically indicated. Additional eye exams may also be performed, as required. Additionally, patients will be carefully monitored for eye complaints at each visit and instructed to report visual symptoms as soon as they occur.

